3.4 Efficacy Assessment

In general, efficacy data will be summarized by treatment group. LFC as measured by MRI-PDFF and cT1 and all other efficacy data will be listed for the ITT Population.

3.4.1 Analyses of LFC as Measured by MRI-PDFF

Summary statistics for LFC at baseline, Week 12/ET and the change and percent change from baseline will be provided for the ITT, mITT and Per-Protocol Populations.

3.4.1.1 Primary Analysis

The primary efficacy outcome measure is the change in the LFC (as measured by MRI-PDFF) from baseline to Week 12/ET.

The primary efficacy analysis will be performed on the ITT Population. Missing MRI-PDFF values at Week 12/ET will be imputed based on the missing at random assumption using multiple imputation. Baseline MRI-PDFF will not be imputed; it is not expected to be missing for any patients.

The multiple imputation procedure and the analysis will be conducted in three separate steps: 1) Multiple Imputation, 2) ANCOVA Model based analysis by Imputed data set, and 3) combination of results using Rubin's rule.

1. Multiple imputation (using SAS PROC MI). Since baseline is required for inclusion and there is only one post-baseline MRI assessment, the missing pattern is monotone. The imputation model will include treatment, stratification factors, and baseline LFC. Note for Part B the baseline LFC is included, and so the LFC stratification factor will not be included in the imputation model. Missing data will be imputed 100 times to generate 100 complete datasets. Sample SAS code is below.

```
*****
Part A:
    TRT01PN: 0=Placebo, 1=Pooled EYP001a
    STRAT1: T2DM (Y, N)
    STRAT2: Statin Use (Y, N)
Part B:
    TRT01PN: 0=Placebo, 1=EYP001a 100 mg QD, 2=EYP001a 200 mg QD
    STRAT1: Statin Use (Y, N)
    STRAT2: Not included
BASE: Baseline LFC
Week12: Week 12/ET LFC
*****
proc mi data=ADEFF seed=345678 n impute=100 out=midatal;
minimum=(. . . . 0) maximum=(. . . . 100);
class TRT01PN STRAT1 STRAT2;
monotone reg(WEEK12 = TRT01PN STRAT1 STRAT2 BASE /details);
var TRT01PN STRAT1 STRAT2 BASE WEEK12;
run;
```

2. Analysis of imputed datasets. Imputed datasets will be analyzed separately using the primary endpoint analysis model. The change in LFC from baseline to Week 12/ET will be analyzed using an analysis of covariance (ANCOVA) model with baseline LFC as a covariate and treatment and stratification groups as factors. Note for Part B the baseline

LFC is included as a covariate, and so the LFC stratification factor will not be included in the ANCOVA model. The least square means (LSMeans) for change from baseline to Week 12/ET LFC within the treatment groups and pairwise differences in LSMeans will be estimated along with their 95% CIs and p-values using Bonferroni method. Sample SAS code is below.

```
*****
Part A:
  TRT01PN: 0=Placebo, 1=Pooled EYP001a
  STRAT1: T2DM (Y, N)
  STRAT2: Statin Use (Y, N)
Part B:
  TRT01PN: 0=Placebo, 1=EYP001a 100 mg QD, 2=EYP001a 200 mg QD
  STRAT1: Statin Use (Y, N)
  STRAT2: Not included
  BASE: Baseline LFC
  CHG: LFC change from Baseline to Week 12/ET
*****
proc mixed data=miout;
by _Imputation_;
class TRT01PN STRAT1 STRAT2;
model CHG = TRT01PN STRAT1 STRAT2 BASE / ddfm=KR;
lsmeans TRT01PN / COV PDIFF CL;
run;
```

3. Combination of estimates across imputed datasets (using SAS PROC MINANALYZE). This will be performed using Rubin's rule and the overall treatment estimates vs. placebo along with their two-sided 95% CI, two-sided 97.5% CI, and p-value will be provided.

```
*****
Part A: TRT01PN: 0=Placebo, 1=Pooled EYP001a
Part B: TRT01PN: 0=Placebo, 1=EYP001a 100 mg QD, 2=EYP001a 200 mg QD
*****
proc mianalyze data=lsmeans;
by TRT01PN;
modeleffects estimate;
stderr stderr;
run;
```

The primary efficacy results will subsequently be analyzed by adding LSM and CAP values at enrollment as additional covariates.

Normality assumptions will be assessed via review of residual plots and non-parametric analyses may be explored if needed.

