1.2.2 Experience in Nonalcoholic Steatohepatitis

After database lock of Part A of the current protocol, EYP001-202, an unscheduled interim analysis was performed on all endpoints collected on the 24 patients enrolled in the Safety Run-in Cohort. The review showed that EYP001a was safe in male and female NASH patients with stage F2 to F3 fibrosis. The most frequent (>20% in any treatment group) treatment-emergent adverse events (TEAEs) were pruritus and nausea. Nausea occurred in 2 of 6 (33.3%) patients in the 400 mg QD dose group, nausea was not experienced by patients in other dose groups. Pruritus reported by Investigators occurred in 5 of 6 (83.3%) patients in the 100 mg BID dose group, 3 of 5 (60.0%) patients in the 200 mg QD dose group, 5 of 6 (83.3%) patients in the 400 mg QD dose group, and no (0%) patients in the placebo group, although 4 of 7 (57.1%) patients in the placebo

group reported pruritus on the visual analog scale. Interestingly, patients receiving the 200 mg QD EYP001a dose reported less intense pruritus (Figure 5).

[figure not shown]
Figure 5. Pruritus Intensity Reported by Patient on the Visual Analogue Scale (0 to 10) Over the Treatment Period (AUC Integrated and Normalized)

AUC = area under the plasma concentration-time curve; BID = twice daily; ITT = Intent-to-Treat; LS = least square; NS = not significant; QD = once daily; SE = standard error.

In the pooled analysis of all EYP001 subjects with pruritus, it appeared that NASH subjects who early-terminated their participation due to pruritus experienced pruritus during the first week, while NASH subjects who completed their participation experienced pruritus later (Figure 6).

Figure 6. Pruritus Onset in Days for Intent-to-Treat Population

ITT = Intent-to-Treat; SD = standard deviation.

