6.5 Early Termination Visit and Withdrawal Procedures (Parts A and B)

The end of treatment for patients completing the study is Day 84 (Week 12).

Patients who discontinue early from the study for any reason before completion of the Treatment Period will be requested to return to the clinic for an ET Visit within a maximum of 48 hours after their last intake of study drug, regardless of how many days they participated in the study.

Patients who discontinue early from the study for any reason after completion of the Treatment Period and before the EOS Follow-up Visit will be requested to return to the clinic for an ET Visit as soon as possible and no later than the planned EOS Follow-up Visit.

For patients who are withdrawn from the study prior to completion, all ET procedures will be performed at an ET Visit. These procedures include the following:

- Record changes in concomitant medications.
- Perform brief physical examination.
- Measure body weight and calculate BMI.
- Measure waist circumference (Part A only).
- Measure waist and hip circumferences (Part B only).
- Calculate WHR and WHtR (Part B only).
- Collect vital signs (systolic and diastolic blood pressure, heart rate, respiratory rate, and body temperature) with the patient in the sitting position after 5 minutes of rest and before any blood draws.
- Administer the AUDIT-C test.
- Counsel on diet/lifestyle.
- Collect blood sample for the following:
 - Chemistry, hematology, coagulation, and lipid and metabolic profile.
 - PD (preferably within 24 to 48 hours of last intake of study drug).
 - Liver fibrosis and inflammation.
 - Serum pregnancy test.

- PK (preferably within 24 to 48 hours of last intake of study drug).
- Plasma storage.
- Collect urine sample for urinalysis.
- Perform 12-lead ECG.
- Perform MRI-PDFF and cT1 imaging only for patients on study drug ≥ 4 weeks.
- Perform FibroScan VCTE (optional).
- Assess pruritus (Part A only).
- Assess adverse events.
- Collect returned used/unused study drug and assess compliance.

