10 STATISTICS

10.1 Analysis Populations

The Intent-to-Treat (ITT) Population includes all patients who are randomized and administered at least 1 dose of study drug. Patients without a Week 12 or end of treatment MRI-PDFF assessment will be imputed as nonresponders unless otherwise specified.

The Safety Population is identical to the ITT Population.

The modified ITT (mITT) Population includes patients from the ITT Population who have valid baseline and Week 12 MRI-PDFF measurements of LFC.

The Per-Protocol Population includes all patients from the mITT Population who finish the 12-week Treatment Period without any major protocol violations. The analysis of LFC as measured by MRI-PDFF will be repeated on the Per-Protocol Population to test the robustness of results.

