10.2.8 Sample Size Determination

The sample size of 114 randomized patients (n = 24 patients in Part A and n = 90 in Part B [n = 30 patients per treatment group]) is based on the efficacy endpoint: absolute change in LFC as measured by MRI-PDFF from baseline to Week 12, assuming that the treatment difference between each active treatment group with placebo is at least 5.1% with a common standard deviation of 5.8%.

With a 2-sample Z-test with the power of 0.8 and an overall family-wise 1-sided alpha of 0.025 (or each active versus placebo alpha = 0.0125 after Bonferroni adjustment), 26 patients per treatment group will be needed to complete the Week 12 Visit. With the consideration of an approximately 13% dropout rate before Week 12, 30 patients will be randomized per treatment group in Part B.

A Lan-DeMets alpha spending function will be used for this group sequential design. Nonbinding O'Brien-Fleming efficacy boundaries and futility boundaries will be calculated using EAST 6.4 software. The efficacy and futility boundaries are described in [Table 6](#).

At the time of the interim analysis, if the test-statistic is equal to or less than the futility boundary, the Sponsor can decide to stop the study due to lack of efficacy.

Table 6. Efficacy and Futility Boundaries for Part B

Look	Week 8 Number of Patients	Week 12 Number of Patients	Information Fraction	Cumulative Alpha Spent	Cumulative Beta Spent	Z Efficacy Boundary	Z Futility Boundary	p-value Efficacy Boundary	p-value Futility Boundary
#1 (interim analysis)	45	23	0.25	<0.0001	0.0113	-4.7604	0.6966	<0.0001	0.7570
#2 (final analysis)	90		1	0.0125	0.1962	-2.2414	-2.2414	0.0125	0.0125

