3.1.7 Hypothesis Testing

Unless stated otherwise, tests will be performed at the nominal alpha one-sided level of 0.025. 95% two-sided confidence intervals (CIs) will also be reported.

In Part A as only the pooled EYP001a treatment group is being compared to placebo, no adjustments for multiplicity are required.

In Part B, to adjust the 2 tests (each EYP001a dose and placebo) for multiplicity in order to control the family-wise type I error at 0.025 one-sided, the Bonferroni method will be used.

3.1.8 *Evaluation of Site Effect*

The number of subjects at each site is expected to be too small to evaluate site effect.

3.1.9 *Handling of Dropouts and Missing Data*

In general, few missing data are expected and, unless stated otherwise, they will not be replaced.

Missing values for the primary Week 12/ET endpoint, LFC, and the key secondary endpoint, cT1, will be imputed based on the missing at random (MAR) assumption using multiple imputation as the primary analysis. A sensitivity analysis for the primary endpoint, LFC, will also be carried out whereby the missing values will be imputed using the multiple imputation with tipping point method based on the missing not at random assumption. Further details of the multiple imputation methods will be provided in the relevant sections below.

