3.4.1.2 Sensitivity Analysis

Sensitivity analyses will be conducted by repeating the primary efficacy analysis based on:

- The ITT Population with missing MRI-PDFF values at Week 12/ET imputed using the multiple imputation with tipping point method based on the missing not at random assumption (further details provided below)
- The mITT Population

- The Per-Protocol Population

Tipping-point analysis

Robustness of the primary analysis results to the departure from the MAR assumption will be explored in the ITT population using the tipping-point analysis based on the pattern mixture model approach.

The considered pattern mixture model will introduce a penalty δ corresponding to the difference in mean change from baseline to Week 12/ET LFC between patients with missing data and patients with observed data.

Estimations will be performed using the same MI approach as described previously. In each treatment group, a penalty δ will be added to the imputed values ($\delta = 0$ corresponds to the MAR assumption) after the PROC MI step. Sample SAS code is below.

```
*****
Part A:
    TRT01PN: 0=Placebo, 1=Pooled EYP001a
    STRAT1: T2DM (Y, N)
    STRAT2: Statin Use (Y, N)
Part B:
    TRT01PN: 0=Placebo, 1=EYP001a 100 mg QD, 2=EYP001a 200 mg QD
    STRAT1: Statin Use (Y, N)
    STRAT2: Not included
&Shifti:  $\delta$ , such as -1 to 1 by 0.1
&Shiftj:  $\delta$ , such as -1 to 1 by 0.1
BASE: Baseline LFC
CHG: Change from Baseline to Week 12/ET LFC
*****
proc mi data=ADEFF seed=345678 n impute=100 out=midatal;
minimum=(. . . . -100) maximum=(. . . . 100);
class TRT01PN STRAT1 STRAT2;
monotone reg;
mnar adjust(CHG / shift=&Shiftj adjust=(TRT01PN='1'))
    adjust(CHG / shift=&Shifti adjust=(TRT01PN='0'));
var TRT01PN STRAT1 STRAT2 BASE CHG;
run;
```

To investigate how the conclusions depend on the adopted values δ , the testing will be repeated over a range of plausible values for the pairs (δ pooled EYP001a, δ Placebo for Part A; δ each EYP001a group, δ Placebo for Part B). The δ values range from -1 to 1 by 0.1, in each treatment group. The δ values may be adjusted depending on the actual data observed. Sample SAS code is below.

```
*****
Part A:
    TRT01PN: 0=Placebo, 1=Pooled EYP001a
    STRAT1: T2DM (Y, N)
    STRAT2: Statin Use (Y, N)
Part B:
    TRT01PN: 0=Placebo, 1=EYP001a 100 mg QD, 2=EYP001a 200 mg QD
    STRAT1: Statin Use (Y, N)
    STRAT2: Not included
```

```
SHIFTEYP:  $\delta$ , such as -1 to 1 by 0.1

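### Patients who leave before Week 4 get no post-baseline MRI and are imputed from their own arm; add one placebo-based sensitivity analysis and a wider delta range, in both active arms, beside the MAR result

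*SAP*

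**What the plan says.** **Who is scanned.** Protocol 6.5 limits imaging at early termination (ET): "Perform MRI-PDFF and cT1 imaging only for patients on study drug ≥ 4 weeks". SAP 3.1.4 repeats the limit. The same protocol section places the ET visit within 48 hours of the last dose for patients who leave during treatment. A patient who leaves before Week 4 therefore has a screening MRI and nothing after it.

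**Who is analysed.** The ITT population (Protocol 10.1, SAP 3.2.2) needs only randomization and one dose, so these patients stay in.

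**How the gap is filled.** SAP 3.4.1.1: "Missing MRI-PDFF values at Week 12/ET will be imputed based on the missing at random assumption using multiple imputation". For Part B the imputation regression has treatment, statin use and baseline LFC. It has no term for stopping drug or for time on drug.

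**Sensitivity analyses (SAP 3.4.1.2).** The primary analysis is repeated on the mITT and Per-Protocol populations, and a tipping-point analysis is planned: "The δ values range from -1 to 1 by 0.1, in each treatment group". The SAP allows this range to be changed in light of the observed data. It also promises the smallest active-arm delta, with placebo delta at 0, that reverses the primary conclusion.

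**Responder endpoints.** Protocol 10.1: "Patients without a Week 12 or end of treatment MRI-PDFF assessment will be imputed as nonresponders unless otherwise specified". SAP 3.4.1.3 applies the same rule.

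**Planned dropout.** Protocol 10.2.8: "With the consideration of an approximately 13% dropout rate before Week 12, 30 patients will be randomized per treatment group in Part B".

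**The concern.** The reason a scan is missing is the early end of treatment itself, and the model that fills it in cannot see this. A patient who stops at Week 3 receives a value typical of the arm's scanned patients. One who stops at Week 5 is counted at the observed ET value. The Week 3 patient is also a nonresponder on every responder endpoint. Neither document states an estimand that would explain the difference.

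Part A gives reason to expect some such patients. Investigators reported pruritus in 60% to 83.3% of patients in the active groups and in none on placebo, and "NASH subjects who early-terminated their participation due to pruritus experienced pruritus during the first week" (Protocol 1.2.2). SAP 4.1 records that 19 patients had completed Week 4 at the first interim analysis, of 24 planned. It does not say whether the other five had left.

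At stake is the size of the headline LFC difference. A reader who takes ITT to mean all assigned patients would credit early leavers with drug benefit that nobody measured, and no planned analysis shows how much the LFC difference would shrink without it.

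**Working it through.** **Inputs.** Effect 5.1 points, SD 5.8, 26 completers and 30 randomized per arm, dropout about 13% (Protocol 10.2.8). For error control, SAP 3.1.7 says "control the family-wise type I error at 0.025 one-sided, the Bonferroni method will be used", and Protocol 10.2.8 gives "each active versus placebo alpha = 0.0125 after Bonferroni adjustment".

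**Assumptions that the documents do not supply.** (a) An active-arm patient who leaves before Week 4 has a placebo-like change at Week 12. (b) The share of dropouts who leave before Week 4 is varied over a quarter, a half and all.

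**The plan's own figure.** n per arm = 2 × (2.2414 + 0.8416)² × (5.8/5.1)² = 24.6, so 25, against the stated 26. Power at 26 is 82.4%. 26/0.87 = 29.9, so 30, as stated. The plan's sizing is reproduced to within one patient.

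**Size of the gap.** Let g be the fraction of the active arm that is unscanned and placebo-like. MAR imputation recovers 5.1. The effect in all assigned patients is 5.1 × (1 − g), so the excess is 5.1 × g. Planned dropout is 4 of 30:

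| Share of dropouts before Week 4 | g | Effect in all assigned | Excess of MAR |
|---|---|---|---|
| A quarter | 1/30 | 4.93 | 0.17 |
| A half | 2/30 | 4.76 | 0.34 |
| All | 4/30 | 4.42 | 0.68 |

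The standard error of a difference is 5.8 × √(2/26) = 1.61, so the excess is about 0.1 to 0.4 standard errors. If early active-arm loss were 5/24 (20.8%), the excess would be 1.06. That applies an all-arm Part A count with unknown reasons to one arm, so it only illustrates dropout above plan.

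**Simulation check.** One active arm versus placebo, 30 per arm, ANCOVA on treatment and baseline, 20 imputations combined by Rubin's rules, 3,000 runs (6,000 under the null):

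- With 4 unscanned per arm, MAR gives -5.13. Complete Week 12 data would give -4.46. Rejection rates at one-sided 0.0125 are 0.81 and 0.71.
- With 6 unscanned on active and 1 on placebo, MAR gives -5.06 and complete data -4.04.
- With no drug effect, MAR rejects in 0.0117 of runs against the nominal 0.0125. Type I error is not inflated.

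**What the stated delta range can show.** A positive delta on an active arm removes benefit. With 4 of 30 unscanned, delta = +1 moves the estimate by 4/30 × 1 = 0.13, from -5.13 to -5.00 in simulation. Reaching placebo-like values takes delta of about 5.1, which moves it by 0.68, from -5.10 to -4.42 in a second run. The stated range covers about a fifth of that distance (1/5.1).

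**What the sample code shifts.** The PROC MI code in SAP 3.4.1.2 adjusts TRT01PN '1' and '0'. In Part B, '2' is 200 mg QD, so as written that arm gets no shift, although the text calls for a delta in each EYP001a group.

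**mITT and Per-Protocol.** Both require a Week 12 or ET scan, so both drop the patients in question and cannot test the assumption made about them.

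**The case against.** The strongest reply is that ITT here names a population, not an estimand. Imputation under MAR is an accepted way to estimate the effect had patients remained on drug, and that is a reasonable question for a Phase 2a proof-of-concept trial. This stands. A reader might infer that the plan's ITT effect is simply overstated. The documents do not support that without the two conditions: the result is read as the effect in all assigned patients, and early leavers keep little benefit. The short plasma half-life does not settle how quickly liver fat returns.

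A reader might also infer that no planned analysis treats these patients as unhelped. The responder analyses do. The delta range can be widened, and the promised reversal delta would usually force it past +1. In a simulation of 400 trials with 4 unscanned per arm, about 80% of the trials significant under MAR needed delta above 5.1 to reverse. What remains is narrower. A reversal delta is a threshold, not an estimate of the LFC difference under no benefit, and the widening is left until data have been seen.

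A third inference is that the comparison of 200 mg with 100 mg is biased towards the less tolerated dose. Both active arms take 100 mg QD through Day 14 (Protocol 3.1), so first-week pruritus arises under identical dosing, and the planned tests are each dose against placebo.

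The Part A evidence is also softer than it looks. The 83.3% rates belong to regimens dropped for Part B. The 200 mg QD figure is 3 of 5 patients, without titration. On the visual analog scale, 4 of 7 placebo patients reported pruritus. The dates and number of early stops are not given, and Part B titrates against pruritus.

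**Conclusion.** The concern holds in a conditional form, as a cheap improvement and not as an error in the primary analysis. The scan rule and the own-arm imputation are in the documents. Read as the effect in all assigned patients, the MAR result is about 0.2 to 0.7 points too large at the planned 13% dropout. This assumes placebo-like Week 12 values after early stopping, and a quarter to all of dropouts before Week 4. The upper figure is a ceiling for that dropout rate, and the excess is larger only if early active-arm loss exceeds plan. Read as the effect had patients remained on treatment, the result needs no correction provided MAR holds. False-positive risk is unaffected under either reading.

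The gap in the plan is that no analysis estimates the LFC difference when early leavers are given no benefit, and that the stated delta range and sample code do not get there.

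**What to change.** Keep the MAR primary analysis and state in SAP 3.4.1.1 that it targets the effect had patients remained on treatment. In SAP 3.4.1.2, before the first database lock:

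1. Add one placebo-based (reference-based) multiple imputation as a sensitivity analysis, for active-arm patients whose Week 12/ET scan is missing because they stopped study drug. Keep MAR for scans missed while on drug. Run these as separate imputation steps: a single MODELOBS statement cannot separate reasons for missingness, and treatment must be removed from the placebo-based regression because its coefficient cannot be estimated from placebo patients alone. Report each dose versus placebo with its two-sided 97.5% CI beside the MAR result.
2. Pre-specify an active-arm delta range reaching at least about +5.1 points, and apply the shift to both active arms (TRT01PN '1' and '2').

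No new patients, scans or data are needed. The cost is a small amount of programming and a less favourable second estimate: about 4.4 to 4.9 in place of 5.1 at 13% dropout, under the assumptions above. The added analysis should be labelled a sensitivity analysis. ET scans after Week 4 are taken within 48 hours of the last dose, so it is not a full treatment-policy estimate.

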SHIFTPBO:  $\delta$ , such as -1 to 1 by 0.1
BASE: Baseline LFC
CHG: LFC change from Baseline to Week 12/ET
*****
proc GLM;
by _Imputation_ SHIFTEYP SHIFTPBO;
class TRT01PN STRAT1 STRAT2;
model CHG = TRT01PN STRAT1 STRAT2 BASE;
lsmeans TRT01PN / CL DIFF STDERR;
estimate "EYP001a vs Placebo" TRT01PN / 1 -1 / E;
run;

proc mianalyze data=diffs;
by SHIFTEYP SHIFTPBO;
modeleffects difference;
stderr stderr;
run;
```

Results will then be summarized using tables and a contour plot of the upper limit of 95% CI of LSMean difference between EYP001a and Placebo arms in change from baseline in LFC at Week 12/ET for the different δ will also be provided.

Then smallest value of δ EYP001a for a value of δ Placebo equal to 0 which will reverse the conclusion for the primary endpoint will be provided.

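### The pooling code printed for the primary analysis (SAP 3.4.1.1, step 3) combines arm means tested against zero, while the text above it promises estimates versus placebo

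*SAP*

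**What the plan says.** The comparison with placebo is stated in several places. Protocol 10.2.1.1 calls for pairwise comparisons of each dose with placebo from the ANCOVA. SAP 3.1.7 counts two such tests in Part B, Bonferroni-adjusted within a one-sided family-wise error of 0.025. In SAP 3.4.1.1, the step 2 text says that "pairwise differences in LSMeans will be estimated along with their 95% CIs and p-values using Bonferroni method", and the step 3 text promises "overall treatment estimates vs. placebo along with their two-sided 95% CI, two-sided 97.5% CI, and p-value will be provided".

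The code for the same analysis runs as follows:

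- Step 2 fits PROC MIXED in each imputed data set with "lsmeans TRT01PN / COV PDIFF CL". This produces two tables: arm LSMeans and all pairwise differences.
- Step 3 pools with "proc mianalyze data=lsmeans", a BY statement on TRT01PN, and "modeleffects estimate". Its header lists "Part B: TRT01PN: 0=Placebo, 1=EYP001a 100 mg QD, 2=EYP001a 200 mg QD".

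The tipping-point code in SAP 3.4.1.2 instead pools with "proc mianalyze data=diffs" and "modeleffects difference".

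**The concern.** PROC MIANALYZE tests each pooled effect against zero unless another null value is given, and none is given here. Fed with arm LSMeans by TRT01PN, it produces three pooled means in Part B, one of them for placebo. Each p-value asks whether that arm changed from baseline. None asks whether a dose differs from placebo.

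That matters for a liver-fat endpoint measured before and after 12 weeks, with diet and lifestyle counselling in every arm. Any fall shared with placebo would count as evidence for the drug, and the standard error would be that of one mean, smaller than that of a difference.

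This is the only pooling code given for the primary analysis. Percent change in LFC (SAP 3.4.1.4) and cT1 (SAP 3.4.1.5) are modelled on the primary analysis, so a programming slip here could carry over to both.

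**Working it through.** **Inputs.** SD 5.8, difference 5.1, one-sided alpha 0.0125 per comparison, power 0.80, 26 completers and 30 randomized per arm, about 13% dropout (Protocol 10.2.8). Placebo change of -0.9 points in a 12-week study of another drug (Protocol Section 1). Shared changes of -2.0 and -3.0 are assumptions, used to show the range.

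**The plan's own figure.** n = 2 × 5.8² × (2.2414 + 0.8416)² / 5.1² = 67.28 × 9.505 / 26.01 = 24.6, so 25 per arm by the Z formula. A noncentral-t calculation gives 26 (power 0.802; 25 gives 0.784). 26 / 0.87 = 29.9, so 30 randomized. The stated sample size is reproduced.

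**Standard errors at 26 per arm.**
- Arm mean (code as printed): 5.8 / √26 = 1.137
- Difference from placebo (text): 5.8 × √(2/26) = 1.609

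**False-positive rate if arm means are pooled.** Suppose there is no drug effect and every arm changes by c. The chance that one active arm gives one-sided p<0.0125 against zero is Φ(−2.2414 − c/1.137). For at least one of two independent arms it is 1 − (1 − p)².

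| Shared change c | One arm | At least one of two |
|---|---|---|
| 0 | 0.0125 | 0.025 |
| -0.9 | Φ(−1.450) = 0.074 | 0.14 |
| -2.0 | Φ(−0.483) = 0.31 | 0.53 |
| -3.0 | 0.65 | 0.88 |

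The test on the difference stays at 0.0125 per comparison whatever c is.

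**Check by simulation.** Multiple imputation, ANCOVA and Rubin's rules were simulated with 30 per arm, 13% missing, 20 imputations and 1,000 trials per setting. For arm means against zero, the one-arm rates were 0.010, 0.079, 0.29 and 0.63. For differences from placebo they were 0.015 to 0.017 throughout.

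**One worked result.** An active change of -3.0 gives z = −3.0/1.137 = −2.64, one-sided p = 0.004, whatever placebo does. Against a placebo change of -0.9, z = −2.1/1.609 = −1.31, p = 0.096. Against -2.0, z = −1.0/1.609 = −0.62, p = 0.27.

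**Would the raw differences table be enough?** Not in Part B. With levels 0, 1 and 2, PDIFF files both 0-versus-1 and 0-versus-2 under TRT01PN = 0. Pooling by TRT01PN would then mix two contrasts, with the sign reversed.

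**The case against.** The strongest reply is that the test is defined by the prose, which is right everywhere it appears. Steps 1 and 2 label their code as samples, and SAP Section 6 puts detailed programming specifications in separate documents that are not available here. The snippets are plainly schematic. PROC MI writes one data set name and PROC MIXED reads another; the change score is not derived after imputation; no output statement is shown; and STRAT2 appears in statements although it is not used in Part B. Within-arm LSMeans are a required output, so the call for the differences may simply have been left out. The tipping-point section asks which shift reverses the primary conclusion and works on differences, which fits only a primary conclusion based on a difference. A placebo p-value in the output would also make the slip visible.

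Most of this stands. A reader might infer that the sponsor planned a one-sample test, or that this code defines the primary test. The documents support neither.

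The reply does not remove the defect. Step 3's code carries no sample label, sits directly under a sentence that it does not implement, and has no companion call for the differences. If it was meant only for within-arm estimates, the SAP prints no pooling code for the primary comparison. The tipping-point code is a guide to intent only: its contrast has two coefficients for Part B's three arms, and its shifts cover only levels 0 and 1.

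**Conclusion.** The printed step 3 code and the step 3 text contradict each other, in the primary analysis, and the code should be corrected. The text has the right comparison.

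The error rates of about 7% and 31% per arm, against 1.25%, hold only if the final program copied the code and its arm-level p-values were then read as comparisons with placebo. They also need a change shared by all arms. The -0.9 comes from a different drug's study, and the -2.0 is assumed. With no shared change, alpha is unaffected.

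Two smaller gaps in the same code are refinements. It sets no alpha level for the promised 97.5% interval. It also gives no complete-data degrees of freedom; with 85 df the normal critical value corresponds to P(t < −2.2414) = 0.0138, so about 1.4% against 1.25% per comparison.

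**What to change.** In step 2, replace the LSMEANS options with `lsmeans TRT01PN / DIFF=CONTROL('0') CL;` and add `ods output diffs=diffs;`. TRT01PN in that table then identifies the active arm, and each estimate is active minus placebo. Sort by TRT01PN and _Imputation_.

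In step 3, run `proc mianalyze data=diffs alpha=0.025; by TRT01PN; modeleffects estimate; stderr stderr;` for the 97.5% interval, and repeat with `alpha=0.05` for the 95% interval. Optionally add `edf=85`: 90 patients less five model parameters (intercept, two treatment terms, statin use, baseline LFC).

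Keep the existing LSMeans call, labelled as descriptive within-arm output. State that percent change in LFC and cT1 use the corrected pooling; for cT1 the optional `edf` must be recomputed, because that model also carries the LFC strata.

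The cost is a few lines of SAP code, with no change to design or data. If the analysis has already been run, check which table the program pooled.
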